6.0 TREATMENT PLAN AND ENTRY PROCEDURE/REGISTRATION PROCEDURE

HIC#: 1603017415 Protocol version 11.0

6.1 Study Entry: Subjects will be screened and consented by the P.I. or a member of the study staff. Consent may be obtained remotely. The consent form can be mailed or emailed to the research participant who will sign a printed version of the consent form and fax/scan/email/send a picture of the signed consent form or mail the signed consent form back to the researcher.

[figure not shown]

FIGURE 1: Study Timeline

6.2 Treatment Plan This is a randomized Phase II, three arm control trial in subjects with CIN 2/3 high grade cervical dysplasia. Subjects with CIN 2/3 meeting eligibility criteria will have cervical biopsy specimens centrally reviewed by study pathologist to confirm diagnosis. HPV DNA test and HPV 16/18 genotyping will be performed from endocervical cytobrush samples to determine HPV status associated with the dysplasia.

Subjects who have CIN 2/3 with HPV+ disease will be enrolled in this study. Subjects will be randomized to one of three arms: observation only (control), imiquimod only, imiquimod + 9-valent HPV vaccine. All cytology and cervical biopsy specimens related to the study will be centrally reviewed by study pathologists who will be blinded to treatment assignment.

6.2.1 Pre-Treatment Visit/Study Enrollment: After the index cervical biopsy demonstrating CIN 2-3, all subjects will be brought back to clinic to discuss results and management. After obtaining informed written consent the following pre-treatment tests will be performed: medical history, physical exam with pelvic exam, vital signs, urine pregnancy test (must be performed within 7 days of treatment), translational blood

HIC#: 1603017415 Protocol version 11.0

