7.2.3.3 Women of Child-Bearing Potential and Pregnancy Prevention

Subjects who are not of childbearing potential due to being postmenopausal (1 year without menstruation) or surgical sterilisation (bilateral oophorectomy and/or tubal ligation) do not need to use contraception to be eligible for the trial.

All other subjects are considered to have childbearing potential and must use adequate contraception throughout the trial (from screening until end of trial participation).

Acceptable methods of contraception include surgical sterilisation and double barrier method, and must be in accordance with local regulations where applicable. Double barrier method of contraception is defined as two barrier methods used simultaneously each time the subject has intercourse. Accepted barrier methods include diaphragm, female condom, cervical cap, male condom and intrauterine device (IUD) (the diaphragm and cervical cap must be used in conjunction with spermicidal jelly/cream). Those using hormonal contraceptives, or with partners using hormonal contraceptives, must also be using an additional approved method of contraception (as described above). Partner vasectomy, natural "rhythm" and spermicidal jelly/cream are not acceptable methods of contraception.

HIC#: 1603017415 Protocol version 11.0

Women who become pregnant while participating in the study must discontinue study medication immediately. The pregnancy must be reported following procedures detailed in section 12.10.2.

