8.2.3.3 Women of Child-Bearing Potential and Pregnancy Prevention

Subjects who are not of childbearing potential due to being postmenopausal (1 year without menstruation) or surgical sterilisation (oophorectomy, hysterectomy and/or tubal ligation) do not need to use contraception to be eligible for the trial.

All other subjects are considered to have childbearing potential and must use adequate contraception throughout the trial (from screening until end of trial participation).

Acceptable methods of contraception include surgical sterilisation and double barrier method, and must be in accordance with local regulations where applicable. Double barrier method of contraception is defined as two barrier methods used simultaneously each time the subject has intercourse. Accepted barrier methods include diaphragm, female condom, cervical cap, male condom and intrauterine device (IUD) (the diaphragm and cervical cap must be used in conjunction with spermicidal jelly/cream). Those using hormonal contraceptives, or with partners using hormonal contraceptives, must also be using an

HIC#: 1603017415 Protocol version 11.0

additional approved method of contraception (as described above). Partner vasectomy, natural "rhythm" and spermicidal jelly/cream are not acceptable methods of contraception.

Women who become pregnant while participating in the study may not receive any additional doses of the HPV vaccine. The pregnancy must be reported following procedures detailed in section 12.10.2.

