or SAE only if the frequency, severity, or character of the condition worsens during the study.

When reporting such events, it is important to convey the concept that the preexisting condition

has changed by including applicable descriptors (e.g., "more frequent headaches").

d. Hospitalizations for Medical or Surgical Procedures

Any AE that results in hospitalization or prolonged hospitalization should be documented and

reported as an SAE.

HIC#: 1603017415

Protocol version 11.0

Version date: December 20, 2022

APPROVED BY THE YALE UNIVERSITY IRB 2/24/2023

CIN 2/3

31

If a subject is hospitalized to undergo a medical or surgical procedure as a result of an AE, the

event responsible for the procedure, not the procedure itself, should be reported as the SAE. For

example, if a subject is hospitalized to undergo coronary bypass surgery, record the heart condition

that necessitated the bypass as the SAE.

Hospitalizations for the following reasons do not require reporting:

Hospitalization or prolonged hospitalization for diagnostic or elective surgical procedures for

preexisting conditions

Hospitalization or prolonged hospitalization required to allow efficacy measurement for the study

or

Hospitalization or prolonged hospitalization for scheduled therapy of the target disease of the

study.

e. Pregnancy

If a female subject becomes pregnant while receiving imiquimod or 9-valent HPV vaccine series

or within 30 days of awareness after the last dose of study drug, a report should be completed and

expeditiously submitted to Yale HIC. Follow-up to obtain the outcome of the pregnancy should

also occur.

Abortion of a pregnancy in a study subject receiving Imiquimod, whether accidental, therapeutic,

or spontaneous, should always be classified as serious, and expeditiously reported as an SAE.

Similarly, any congenital anomaly/birth defect in a child born to a female subject exposed to

imiquimod or 9-valent HPV vaccine should be reported as an SAE.

f. Post-Study Adverse Events

The investigator should expeditiously report any SAE occurring after a subject has completed or

discontinued study participation if attributed to prior Imiquimod or 9-valent HPV vaccine

exposure.

If the investigator should become aware of the development of cancer or a congenital anomaly in

a subsequently conceived offspring of a female subject who participated in the study, this should

be reported as an SAE.

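### Section 12.10.2e gives no pregnancy-report trigger for the observation arm or for late post-dose conceptions, and makes pregnancy loss automatically serious only under imiquimod

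*Combined protocol and SAP*

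**What the plan says.** The trial has three arms (section 6.2): "observation only (control), imiquimod only, imiquimod + 9-valent HPV vaccine". Section 6.2.2 and the table in section 9.1 schedule a urine pregnancy test at every follow-up visit and exclude no arm.

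Two sections refer pregnancies onward:

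- Section 7.2.3.3 (imiquimod): "Women who become pregnant while participating in the study must discontinue study medication immediately". It continues: "The pregnancy must be reported following procedures detailed in section 12.10.2".
- Section 8.2.3.3 (vaccine): "Women who become pregnant while participating in the study may not receive any additional doses of the HPV vaccine", followed by the same referral.

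The paragraph they lead to, 12.10.2e, sets its reporting condition as "If a female subject becomes pregnant while receiving imiquimod or 9-valent HPV vaccine series", extended by "or within 30 days of awareness after the last dose of study drug, a report should be completed and" sent promptly to the Yale committee, with follow-up to the outcome of the pregnancy. On loss, the rule begins "Abortion of a pregnancy in a study subject receiving Imiquimod, whether accidental, therapeutic". The sentence then closes with one classification for every kind of loss it lists: "or spontaneous, should always be classified as serious, and expeditiously reported as an SAE".

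Three other provisions bear on the point. Section 13.1 defines an SAE without reference to arm. Section 12.9.4 starts the AE reporting period once consent is given and study treatment begins. Section 15.4 reports SAEs by treatment group on the safety analysis set, which by section 15.2 can include untreated controls.

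**The concern.** The referring rules speak of women in the study, while the rule they rely on speaks of women on study drug. A control who becomes pregnant is found by the trial's own test, but no provision then asks for a report or for follow-up of the outcome. The same holds for a treated woman who conceives late, after the post-dose period has closed but before her last visit.

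The loss rule adds a difference between arms. Whether a given miscarriage is an SAE can depend on whether the woman was given imiquimod, and the resulting counts are shown side by side by treatment group. What is at stake is a clean reading of one event type in the safety table, and complete outcome information on pregnancies that the trial detects.

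**Working it through.** The plan states no figure on this point, so there is nothing to reproduce. The check compares the texts, then works out the window and the scale.

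**1. Who has a trigger under 12.10.2e**

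| Situation | Referred by 7.2.3.3 / 8.2.3.3 (pregnant during participation) | Covered by 12.10.2e |
|---|---|---|
| Conceives while on imiquimod or the vaccine series | Yes | Yes, whenever detected |
| Treated, conceives 1 to 30 days after last dose | Yes | Depends on how the 30 days are read |
| Treated, conceives more than 30 days after last dose, before final visit | Yes | No |
| Observation control | Yes on the wording, though the sentences assume study drug | No |

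**2. The post-dose window**

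Inputs: a 16-week imiquimod course (section 6.2.1), a final visit at weeks 20-24, nominally 22 (sections 1.1 and 6.2.2), and a 30-day period (12.10.2e).

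Days from end of course to final visit = (visit week − 16) × 7:
- week 20: 28 days
- week 22: 42 days
- week 24: 56 days

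*If the 30 days run to conception*, the uncovered stretch before the final visit is max(0, days − 30): 0, 12 and 26 days respectively.

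*If the 30 days run to awareness*, the window closes at week 16 + 30/7 = 20.3. A conception after the last dose that is first found at week 22 (day 42) is then missed, even if it occurred soon after that dose.

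Both results assume that dosing ends at week 16. Section 6.2.1 allows the dosing period to be extended, and section 6.2.2 needs only 3 weeks (21 days) between last dose and final visit. A woman seen within 30 days of her last dose has no gap.

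**3. Seriousness of a loss**

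Section 13.1 covers death, threat to life, hospitalisation, disability, congenital anomaly, and events judged medically to need intervention to prevent one of these. A loss that meets any of these criteria is an SAE in every arm. A loss that meets none is an SAE by rule under 12.10.2e in an imiquimod-treated woman, and not in a control. Both active arms receive imiquimod, so the difference lies mainly between control and active. Taken literally, the word *receiving* would rarely apply, because 7.2.3.3 has a pregnant woman stop study medication at once. I therefore take the rule to mean women treated with imiquimod, but the text should say so.

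**4. Scale**

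Arm size is 46 (section 15.8: 138 in total). The documents give no pregnancy or loss rates. I assume that 1-5% of women become pregnant and that 10-30% of pregnancies end in loss.

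- Expected pregnancies per arm: 46 × 0.01 = 0.46 to 46 × 0.05 = 2.3.
- Expected losses per arm: 46 × 0.01 × 0.10 = 0.046 to 46 × 0.05 × 0.30 = 0.69.
- Chance of at least one loss in an arm, 1 − (1 − q)^46: q = 0.001 gives 0.045; q = 0.015 gives 0.501.

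**The case against.** The strongest reply is that reporting based on exposure is a coherent choice. Sections 7.2.3.3 and 8.2.3.3 sit in the imiquimod and vaccine chapters, and their sentences speak of stopping medication or withholding further vaccine, so they can be read as addressed to treated women. Section 12.9.1 likewise centres on drug-related events, and no objective in section 1 concerns pregnancy outcome. This stands far enough that the defect is a mismatch of scope. A reader might infer an outright contradiction, but the texts do not go that far. The reply does not remove the mismatch: the same two subsections require contraception of all women of childbearing potential until trial participation ends, and paragraph 12.10.2f covers an anomaly in later offspring of any participant, controls included.

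Other stronger readings also fail:

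- *SAE counts as a whole cannot be compared between arms.* Section 13.1 applies to every arm. Only losses that meet none of its criteria are classified differently, and section 15.6 treats safety descriptively.
- *Control pregnancies vanish from the data.* Section 9.1 requires test results to be recorded, and section 15.4 lists clinical tests by group. What is missing is the report to the committee and the stated outcome follow-up.
- *A pregnancy begun during dosing but found at week 22 is missed.* The first condition of 12.10.2e covers it, whenever it is detected.
- *Elective termination is named as serious.* The text lists accidental, therapeutic and spontaneous abortion only.
- *One or two women per arm would change the SAE table.* That is about the number of pregnancies to expect. The seriousness rule acts on losses, which are fewer.

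**Conclusion.** The point holds as a low-importance defect of wording. Section 12.10.2e has no report or follow-up trigger for the observation arm, one third of the trial (46 of 138 planned). It also leaves up to 26 days before the final visit uncovered for treated women who finish at week 16 (12 days at the nominal week 22), and its 30-day clause has no single reading. Its seriousness rule for pregnancy loss differs between control and imiquimod-treated women for losses outside section 13.1.

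The size is small: 0.05 to 0.69 expected losses per arm under the assumed rates, and fewer that meet no section 13.1 criterion. No efficacy objective, hypothesis test or sample size is affected. The conclusion about the text does not depend on the assumed rates; only the scale does.

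**What to change.** Reconcile 12.10.2e with 7.2.3.3 and 8.2.3.3:

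1. State one window for pregnancy reporting and outcome follow-up, from randomisation to the final study visit, in all three arms.
2. For the active arms, keep the 30-day post-dose period in addition. Define it by date of conception, so that it applies whenever the pregnancy is detected.
3. Apply one seriousness rule for pregnancy loss to all arms.
4. Align section 12.9.4, whose reporting period begins with study treatment and so has no clear start for controls. Without this step, rewording 12.10.2e alone would leave SAE capture tied to drug administration.

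The cost is protocol wording. The urine tests are already scheduled in every arm, and the added workload is about one or two more pregnancy reports.

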13.0 PROCEDURES FOR REPORTING UNANTICIPATED PROBLEMS INVOLVING RISKS

TO SUBJECTS OR OTHERS, INCLUDING ADVERSE EVENTS (UPIRSOs)

HIC#: 1603017415

Protocol version 11.0

Version date: December 20, 2022

APPROVED BY THE YALE UNIVERSITY IRB 2/24/2023

13.1 Expedited Reporting of UPISROs Occurring at Yale

AEs classified as "serious" and "unexpected" that are possibly, probably, or definitely attributed to drug administration, or SAEs whose frequency exceeds expectations, require expeditious handling and reporting.

Serious Adverse Event (SAE)

Any adverse event that results in any of the following outcomes:

- death.
- a life-threatening experience,
- inpatient hospitalization or prolongation of existing hospitalization,
- a persistent or significant disability/incapacity,
- a congenital anomaly/birth defect, or
- any other adverse event that, based upon appropriate medical judgment, may jeopardize the subject's health and may require medical or surgical intervention to prevent one of the other outcomes listed in this definition.

The PI will promptly investigate all safety information related to an adverse experience. If the results of the PI's investigation show an adverse drug experience not initially determined to be reportable (based on whether the event is serious, unexpected, and associated with drug administration) is so reportable, the PI will report such experience. Follow-up information to a safety report shall be submitted as soon as the relevant information is available.

Reporting to the Yale Human Investigation Committee

Timeframe for Reporting

- 1. Events that may require a temporary or permanent interruption of study activities by the Principal Investigator or sponsor to avoid potential harm to subjects should be reported to the IRB **immediately** (if possible), followed by a written report to the IRB using the UPIRSO Reporting Form (710 FR 4) **no more than 5 calendar days** after the Yale Principal Investigator becomes aware of the event.
- 2. Internal Events (defined above) should be reported to the IRB using the UPIRSO Reporting Form (710 FR 4) within 5 calendar days of the Principal Investigator becoming aware of the event.
- 3. External Events (defined above) should be reported to the IRB using the UPIRSO Reporting Form (710 FR 4) **within 15 calendar days** of the Yale University Principal Investigator (PI) becoming aware of the event ONLY IF either of the following are true:
 - (a) The Yale PI has concluded that an immediate change to the protocol is necessary to address the risks raised by the event, and BI agreed to the changes OR
 - (b) A monitoring entity (e.g., an external IRB at the site where the problem or event occurred, the sponsor, or the Data Safety Monitoring Board) has required modifications/amendments to the research protocol or consent documents as a result of the event.

HIC#: 1603017415 Protocol version 11.0

CIN 2/3 33

For all reports of external events, the UPIRSO Reporting Form (710 FR 4) must include the following information:

- (a) a clear explanation of why the event or series of events has been determined to meet criteria for reporting;
- (b) a description of the proposed protocol changes and any corrective actions to be taken by the PI in response to the external event; and
- (c) any aggregated data and an analysis or summary from the sponsor or DSMB, when applicable and available, sufficient to explain the significance of the event or series of events in order to ensure the information is interpretable and relevant to the IRB's task of protecting the rights and welfare of human participants.

MedWatch 3500A Reporting Guidelines:

In addition to completing appropriate subject demographic and suspect medication information, the report should include the following information within the Event Description (section 5) of the MedWatch 3500A form:

- Protocol description (and number, if assigned)
- Description of event, severity, treatment, and outcome if known
- Supportive laboratory results and diagnostics

Investigator's assessment of the relationship of the adverse event to each investigational product and suspect medication

Follow-up information:

Additional information may be added to a previously submitted report by any of the following methods:

- Adding to the original MedWatch 3500A report and submitting it as follow-up
- Adding supplemental summary information and submitting it as follow-up with the original MedWatch 3500A form

Summarizing new information and faxing it with a cover letter including subject identifiers (i.e. D.O.B. initial, subject number), protocol description and number, if assigned, brief adverse event description, and notation that additional or follow-up information is being submitted (The subject identifiers are important so that the new information is added to the correct initial report)

MedWatch 3500A (Mandatory Reporting) form is available at http://www.fda.gov/medwatch/getforms.html

At all times, the Remote Monitoring Coordinator is available to facilitate submissions and answer any questions regarding the process for all sub site staff.

HIC#: 1603017415 Protocol version 11.0

CIN 2/3 34

14.0 STUDY MANAGEMENT AND COORDINATION

14.1 Overview

This is a single site trial where **[name]** is the Principal Investigator. The research team at Yale University consisting of a Site Research Coordinator, Data Manager, Clinical Research Nursing Coordinator, Specimen Procurement Coordinator and an Administrative Assistant will provide research support. The YCCI clinical trials management support staff will provide clinical database systems support and training through the use of Oncore Clinical Trials Management System.

14.2. Data Collection

Study will use Oncore Clinical Trials Management System for all data associated with the protocol. Data manager will receive Oncore access, complete an Oncore access request and submit HIPAA training certification. Individuals will receive Oncore training by a member of the YCCI clinical trials management support staff. Subjects entered into the system will be identified by a subject number assigned after randomization. The confidentiality of records that could identify subjects will be protected, respecting the privacy and confidentiality rules in accordance with the applicable regulatory requirement(s).

14.3 Study Enrollment Procedures

Any modification of the original consent document must be approved in advance by the IRB. Rationale will be provided with any request for a change. A copy of the IRB and approved informed consent document must be on file at the Regulatory office before subjects may be enrolled.

To register eligible subjects on this study, contact the Site Coordinator; [name] [contact]) or [name] [contact]) and provide the signed and dated eligibility checklist, completed signature page of the consent form and additional source documents if requested by the Principal Investigator or Site Coordinator verifies eligibility, a unique subject study number will be issued. The subject will not be identified by name.

14.4 Responsibilities of the Principal Investigator [name]:

The principal investigator is responsible for the overall conduct of the study and for monitoring the safety and quality of the data as well as compliance to the protocol and with applicable federal regulations and Good Clinical Practice (GCP).

The principal investigator will monitor accrual rates for adequate progress.

The principal investigator will ensure appropriate coordination, submission and approval of the protocol as well as the consent documents and any subsequent amendments. There will be only one version of these documents and the principal investigator is responsible for assuring that the correct versions are used.

In addition, this study is subject to YCC Discovery Fund Grant Oversight. The principal investigator will provide periodic reports to YCC leadership and attend meetings in accordance with the YCC Discovery Fund Grant Monitoring Plan to ensure study progress toward milestones and timelines are being achieved.

